6.3.6.2. Serious Adverse Events and AESIs

6.3.6.2.1. Main Analyses

- Estimand: The percentage of infant participants reporting SAEs and AESIs (major congenital anomalies, developmental delay) from birth through 6 months of age ([Section 2.1](#)).
- Analysis set: Safety population (infant) ([Section 4](#)) by breastfeeding status.
- Analysis time point: Birth through 6 months of age.
- Analysis methodology: Descriptive statistics ([Section 5.2.1](#)).
- Intercurrent events and missing data: Missing data will not be imputed except for partial SAE start dates ([Section 5.3](#)).
- Reporting results: Counts, percentages, and the associated Clopper-Pearson 95% CIs for infant participants with SAEs and AESIs from birth through 6 months of age will be provided for each vaccine group (according to the study intervention the maternal participants received).

6.3.7. COVID-19 Incidence Rate (Infant Participants)

6.3.7.1. COVID-19 Incidence per 1000 Person-Years of Follow-Up Based on Central Laboratory or Locally Confirmed NAAT

6.3.7.1.1. Main Analyses

- Estimand:
 - COVID-19 incidence based on central laboratory or locally confirmed NAAT per 1000 person-years of follow-up in infants born to maternal participants from each vaccine group ([Section 2.1](#)).
- Analysis set: All-available efficacy population (infant) ([Section 4](#)).
- Analysis time point: End of the surveillance period.
- Analysis methodology: Incidence rate (per 1000 person-years of follow-up) and 2-sided 95% CI for confirmed COVID-19 illness (using the first definition in [Appendix 2](#)) for infants born to maternal participants from each vaccine group.
- Intercurrent events and missing data: Missing data will not be imputed.

- Reporting results: Counts, incidence of COVID-19 per 1000 person-years of follow-up, and the associated 2-sided 95% CIs will be provided for each vaccine group (according to the study intervention the maternal participants randomized).

6.3.7.1.2. Supplemental Analyses

The same analyses will be performed for confirmed COVID-19 illness (using the second definition in [Appendix 2](#)).

6.3.8. MIS-C Cases (Infant Participants)

6.3.8.1. MIS-C Incidence per 1000 Person-Years of Follow-Up

6.3.8.1.1. Main Analyses

- Estimand:
 - MIS-C incidence per 1000 person-years of follow-up in infants born to maternal participants from each vaccine group ([Section 2.1](#)).
- Analysis set: All-available efficacy population (infant) ([Section 4](#)).
- Analysis time point: End of the surveillance period.
- Analysis methodology: Incidence rate (per 1000 person-years of follow-up) and 2-sided 95% CI for confirmed MIS-C cases (see [Appendix 2](#) for the definition) for infants born to maternal participants from each vaccine group.
- Intercurrent events and missing data: Missing data will not be imputed.
- Reporting results: Counts, incidence of MIS-C per 1000 person-years of follow-up, and the associated 2-sided 95% CIs will be provided for each vaccine group (according to the study intervention the maternal participants randomized).

6.4. Other Endpoints

The safety data and immunogenicity results for individuals with confirmed stable HIV disease will be summarized descriptively. Furthermore, VE may be assessed if there is a sufficient number of COVID-19 cases in this group of participants.

For maternal participants, the AEs, including SAEs, reported in the open-label follow-up period will be summarized separately from those reported during the blinded follow-up period.

6.5. Subset Analysis

Subgroup analyses based on race and ethnicity will be performed on all primary safety and immunogenicity endpoints (as supplemental analyses).

6.6. Baseline and Other Summaries and Analyses

6.6.1. Baseline Summaries

6.6.1.1. Demographic Characteristics

For maternal participants, demographic characteristics, including age at Dose 1, race, ethnicity, and classification of BMI, will be summarized for the safety population (maternal) for each vaccine group and overall.

For infant participants, demographic characteristics, including sex, race, ethnicity, and gestational age at birth, will be summarized for the safety population (infant) for each vaccine group and overall.

6.6.1.2. Medical History

For maternal participants, each reported medical history term will be mapped to a SOC and PT according to MedDRA. The number and percentage of vaccinated maternal participants having at least 1 diagnosis, overall and at each SOC and PT level, will be summarized by vaccine group for the safety population (maternal).

The number and proportion of maternal participants with comorbidities that increase the risk for severe COVID-19 illness will be summarized by each vaccine group.

6.6.2. Study Conduct and Participant Disposition

6.6.2.1. Participant Disposition

The number and percentage of randomized maternal participants and their infant participants will be included in the maternal and infant participant disposition summary, respectively.

For maternal participants, the numbers and percentages of participants who received vaccinations (Doses 1 and 2 for both vaccine groups, Doses 3 and 4 for the original placebo group), who completed the follow-up visits (1 month after Dose 2, at delivery, 1 month after delivery, 6 months after delivery for the original active group, 1 month after Dose 4 for the original placebo group), and who withdrew before each follow-up visit, along with the reasons for withdrawal, will be tabulated by vaccine group (according to randomized group assignment). The reasons for withdrawal will be those as specified in the database.

For infant participants, the number of participants who completed the study (6 months after birth) and who withdrew from the study, along with the reasons for withdrawal, will be tabulated by vaccine group (according to the study intervention the maternal participants randomized). The reasons for withdrawal will be those as specified in the database.

Participants excluded from each analysis population will also be summarized separately, along with the reasons for exclusion, by vaccine group.

6.6.2.2. Blood Samples for Assay

The number and percentage of randomized maternal participants and their infant participants providing blood samples within and outside of protocol-specified time frames will be tabulated separately for each time point.

6.6.2.3. Transmission of E-Diaries

The numbers and percentages of vaccinated maternal participants not transmitting the e-diary, transmitting the e-diary for each day, and transmitting the e-diary for all days in the required reporting period will be summarized by as-received vaccine group for each dose.

The safety population (maternal) will be used.

6.6.3. Study Vaccination Exposure

6.6.3.1. Vaccination Timing and Administration

For each dose, the number and percentage of maternal participants randomized and receiving each study intervention within the protocol-specified time frame, as well as before and after the specified time frame, will be tabulated for each vaccine group and overall for all randomized maternal participants. The denominator for the percentages is the total number of randomized maternal participants in the given vaccine group or overall.

In addition, the relation of randomized vaccine to vaccine actually received will be presented as a cross tabulation of the vaccine actually received versus the randomized vaccine.

A listing of maternal participants showing the randomized vaccine and the vaccine actually received at each dose will be presented.

6.6.4. Prior/Concomitant Vaccination and Concomitant Medications

Each prior/concomitant vaccine will be summarized according to the ATC 4th-level classification.

For maternal participants, all vaccines received within 14 days before Dose 1 will be listed. The number and percentage of maternal participants receiving each concomitant vaccine after Dose 1 will be tabulated by vaccine group. The safety population (maternal) will be used. Concomitant medications for maternal participants will be summarized in a similar way as concomitant vaccines.

For infant participants, all concomitant medications received from birth will be listed. The number and percentage of infant participants receiving each concomitant medication after birth will be tabulated by vaccine group. The safety population (infant) will be used.

6.7. Safety Summaries and Analyses

Local reaction, systemic event, AE, and SAE summaries and analyses are described under Primary Safety Endpoints (Section 6.1.1).

7. INTERIM ANALYSES

No formal interim analysis will be conducted for this study. Statistical analyses will be carried out when the final data for specified objectives are available while the study is ongoing. The timing of these planned analysis and reporting events is described in the section below.

7.1. Analysis Timing

Statistical analyses will be carried out when the following data are available:

- Immunogenicity data through 1 month after Dose 2 from all randomized maternal participants for assessment of SARS-CoV-2 neutralizing titers.
- Complete safety, immunogenicity, and efficacy analysis after complete data are available or at the end of the study.

Additional analyses may be conducted if required for regulatory purposes. All analyses conducted while the study is ongoing will be performed by an unblinded statistical team.

7.2. Data Monitoring Committee

This study will use an IRC, a DMC, and a group of internal case reviewers. The IRC is independent of the study team and includes only internal members. The DMC is independent of the study team and includes only external members. The IRC and DMC charters describe the roles of the IRC and DMC in more detail.

The DMC will be responsible for ongoing monitoring of the safety of participants in the study according to the charter. The recommendations made by the DMC to alter the conduct of the study will be forwarded to the appropriate Pfizer personnel for final decision. Pfizer will forward such decisions, which may include summaries of aggregate analyses of safety data, to regulatory authorities, as appropriate.

9. APPENDICES

Appendix 1. List of Abbreviations

Abbreviation	Term
AE	adverse event
AESI	adverse event of special interest
ALT	alanine aminotransferase
ARDS	adult respiratory distress syndrome
ATC	Anatomic Therapeutic Chemical
BiPaP	bilevel positive airway pressure
BLQ	below the limit of quantitation
BMI	body mass index
BNP	brain natriuretic peptide
BP	blood pressure
CDC	Centers for Disease Control and Prevention (United States)
CI	confidence interval
COVID-19	coronavirus disease 2019
CPaP	continuous positive airway pressure
CRF	case report form
CRP	C-reactive protein
CVA	cerebrovascular accident
DBP	diastolic blood pressure
DMC	data monitoring committee
ECMO	extracorporeal membrane oxygenation
e-diary	electronic diary
ESR	erythrocyte sedimentation rate
FiO ₂	fraction of inspired oxygen
GI	gastrointestinal
GM	geometric mean
GMC	geometric mean concentration
GMFR	geometric mean fold rise
GMR	geometric mean ratio
GMT	geometric mean titer
HIV	human immunodeficiency virus
HR	heart rate
ICD	informed consent document
ICU	intensive care unit
IgG	immunoglobulin G
IL-6	interleukin 6
IRC	internal review committee
IRR	illness rate ratio
IWR	interactive Web-based response
LDH	lactate dehydrogenase
LLOQ	lower limit of quantitation
LS	least squares
MedDRA	Medical Dictionary for Regulatory Activities
MIS-C	multisystem inflammatory syndrome in children

Abbreviation	Term
mITT	modified intent-to-treat
N	SARS-CoV-2 nucleoprotein
N/A	not applicable
NAAT	nucleic acid amplification test
PaO ₂	partial pressure of oxygen, arterial
PT	preferred term
RCDC	reverse cumulative distribution curve
RNA	ribonucleic acid
RR	respiratory rate
RT-PCR	reverse transcription–polymerase chain reaction
S	spike protein
SAE	serious adverse event
SAP	statistical analysis plan
SARS-CoV-2	severe acute respiratory syndrome coronavirus 2
SBP	systolic blood pressure
SOC	system organ class
SpO ₂	oxygen saturation as measured by pulse oximetry
ULN	upper limit of normal
VE	vaccine efficacy
WHO	World Health Organization

Appendix 2. IRR and VE Derivation

COVID-19 Case Definition

Maternal Participants

Two definitions of SARS-CoV-2–related cases, and SARS-CoV-2–related severe cases, will be considered (for both, the onset date of the case will be the date that symptoms were first experienced by the maternal participant; if new symptoms are reported within 4 days after resolution of all previous symptoms, they will be considered as part of a single illness):

Confirmed COVID-19, first definition: presence of at least 1 of the following symptoms and SARS-CoV-2 NAAT-positive during, or within 4 days before or after, the symptomatic period, either at the central laboratory or at a local testing facility (using an acceptable test):

- Fever;
- New or increased cough;
- New or increased shortness of breath;
- Chills;
- New or increased muscle pain;
- New loss of taste or smell;
- Sore throat;
- Diarrhea;
- Vomiting.

The second definition, which may be updated as more is learned about COVID-19, will include the following additional symptoms defined by the CDC (listed at <https://www.cdc.gov/coronavirus/2019-ncov/symptoms-testing/symptoms.html>):

- Fatigue;
- Headache;
- Nasal congestion or runny nose;
- Nausea.

Confirmed Severe COVID-19, first definition: confirmed COVID-19 and presence of at least 1 of the following:

- Clinical signs at rest indicative of severe systemic illness (RR \geq 30 breaths/min, HR \geq 125 beats/min, SpO₂ \leq 93% on room air at sea level, or PaO₂/FiO₂ <300 mm Hg);
- Respiratory failure (defined as needing high-flow oxygen, noninvasive ventilation, mechanical ventilation, or ECMO);
- Evidence of shock (SBP <90 mm Hg, DBP <60 mm Hg, or requiring vasopressors);
- Significant acute renal, hepatic, or neurologic dysfunction*;
- Admission to an ICU;
- Death.

The second definition, which may be updated as more is learned about COVID-19, will include the following additional outcomes defined by the CDC (listed at <https://www.cdc.gov/coronavirus/2019-ncov/need-extra-precautions/people-with-medical-conditions.html>):

- Hospitalization;
- Admission to the ICU;
- Intubation or mechanical ventilation;
- Death.

Infant Participants

Two definitions of SARS-CoV-2–related cases, and SARS-CoV-2–related severe cases, will be considered (for both, the onset date of the case will be the date that symptoms were first experienced by the infant participant; if new symptoms are reported within 4 days after resolution of all previous symptoms, they will be considered as part of a single illness). Signs and symptoms of an acute respiratory illness will not be considered a potential COVID-19–related illness if they occur within the first 72 hours after birth.

Confirmed COVID-19, first definition: presence of at least 1 of the following symptoms and SARS-CoV-2 NAAT-positive during, or within 4 days before or after, the symptomatic period, either at the central laboratory or at a local testing facility (using an acceptable test):

- Fever;
- New or increased cough;
- New or increased shortness of breath;

- Diarrhea;
- Vomiting.

The second definition, which may be updated as more is learned about COVID-19, will include the following additional symptoms defined by the CDC (listed at <https://www.cdc.gov/coronavirus/2019-ncov/symptoms-testing/symptoms.html>) but does not trigger a potential COVID-19 illness visit unless, in the opinion of the principal investigator, it is deemed necessary:

- Nasal congestion or runny nose;
- Poor appetite or poor feeding;
- Abdominal pain (colic).

Confirmed Severe Infant COVID-19 definition: confirmed COVID-19 and presence of at least 1 of the following:

- Clinical signs at rest indicative of severe systemic illness:
 - RR (breaths/min): >50 from birth to 1 week of age, ≥ 40 from 1 week to 1 month of age, ≥ 34 from 1 month to 6 months of age;
 - HR (beats/min): >180;
 - SpO₂ $\leq 92\%$ on room air or >50% FiO₂ to maintain $\geq 92\%$, or PaO₂/FiO₂ <300 mm Hg³;
- Respiratory failure (defined as needing high-flow oxygen, including nasal CPaP/BiPaP, noninvasive ventilation, mechanical ventilation, or ECMO);
- Evidence of shock or cardiac failure:
 - SBP (mm Hg) (<5th percentile for age):
 - <65 from birth to 1 week of age, <75 from 1 week to 1 month of age, <100 from 1 month to 6 months of age;

OR

- Requiring vasoactive drugs to maintain BP in the normal range;
- Significant acute renal failure: serum creatinine >2 times ULN for age or 2-fold increase in baseline creatinine;
- Significant GI/hepatic failure: total bilirubin >4 mg/dL or ALT 2 times ULN for age;

- Significant neurologic dysfunction: Glasgow Coma Scale score <11 or acute change in mental status with a decrease in Glasgow Coma Scale score ≥ 3 points from abnormal baseline;
- Admission to an ICU;
- Death.

Confirmed Multisystem Inflammatory Syndrome in Children (MIS-C) definition⁴:
as per the CDC MIS-C case definition:

- An infant presenting with fever ($\geq 38.0^{\circ}\text{C}$ for ≥ 24 hours or report of subjective fever lasting ≥ 24 hours); AND
- Laboratory evidence of inflammation (based on local laboratory ranges) including, but not limited to, 1 or more of the following: an elevated CRP, ESR, fibrinogen, procalcitonin, D-dimer, ferritin, LDH, or IL-6, elevated neutrophils, reduced lymphocytes, and low albumin; AND
- Evidence of clinically severe illness requiring hospitalization (definition as noted above for severe disease), with multisystem (≥ 2) organ involvement:
 - Cardiac (eg, shock, elevated troponin, elevated BNP, abnormal echocardiogram, arrhythmia);
 - Renal (eg, acute kidney injury or renal failure);
 - Respiratory (eg, pneumonia, ARDS, pulmonary embolism);
 - Hematologic (eg, elevated D-dimers, thrombophilia, or thrombocytopenia);
 - GI/hepatic (eg, elevated bilirubin, elevated liver enzymes, or diarrhea);
 - Dermatologic (eg, rash, mucocutaneous lesions);
 - Neurological (eg, CVA, aseptic meningitis, encephalopathy); AND
- No alternative plausible diagnoses; AND
- Positive for current or recent SARS-CoV-2 infection by RT-PCR, serology, or antigen test; OR
- COVID-19 exposure within the 4 weeks prior to the onset of symptoms.

The following are applicable for both maternal and infant participants:

The DMC may recommend modification of the definition of severe disease according to emerging information.

* A small group of blinded case reviewers (medically qualified Pfizer staff members) will review all potential COVID-19 illness events. If a NAAT-confirmed case in Phase 2/3 may be considered severe, or not, solely on the basis of these criteria, the blinded data will be reviewed by the case reviewers to assess whether the criterion is met; the majority opinion will prevail.

In addition, a serological definition will be used for participants without clinical presentation of COVID-19:

- Confirmed seroconversion to SARS-CoV-2 without confirmed COVID-19: a positive N-binding antibody result in a participant with a prior negative N-binding antibody result.

Surveillance Times

Fundamental to VE assessment is the surveillance, for each participant, for cases satisfying various endpoints that may occur during the trial. Endpoint and participant combinations where surveillance is applicable require identification of the start and the end of the surveillance period in order to determine the participant-level endpoint surveillance time. For all COVID-19 VE-related endpoints in this study, the start-of-surveillance times are summarized as follows:

Endpoint's Associated Participant-Level Population	Start-of-Surveillance Time
Evaluable efficacy (maternal)	Dose 2 + 7 days
Dose 2 all-available efficacy (maternal)	Dose 2 + 7 days
Dose 1 all-available efficacy (mITT) (maternal)	Dose 1

For all COVID-19 VE-related endpoints in this study, the end of a surveillance period for each participant is the earliest of the following events:

- When the first COVID-19 case occurs.
- When the participant's end of the study occurs (eg, because of withdrawal, death, or trial completion).
- When the participant has his or her first important protocol violation.
- When the participant is unblinded at 1 month after delivery.

For descriptive assessment of exploratory endpoints of COVID-19 incidence rate (maternal and infant), the surveillance period is defined the same way except that unblinding at 1 month after delivery will not be considered as the end of the surveillance period.

[figure not shown]

Specific information regarding VE-related endpoint surveillance start and end times by endpoint will be provided in Analysis and Reporting Plan specification documents.

Once the COVID-19 cases and surveillance period have been identified, VE can be calculated as $100 \times (1 - \text{IRR})$, where IRR is the ratio of confirmed COVID-19 illness per 1000 person-years of follow-up for the active vaccine group to the placebo group.

[figure not shown]
Flowcharts

1. The flowchart for deriving the COVID-19 cases included below for the first VE endpoint in evaluable efficacy participants with no serological or virological evidence of past SARS-CoV-2 infection:

The central laboratory NAAT result will be used for the case definition, unless no result is available from the central laboratory, in which case a local NAAT result may be used if it was obtained using 1 of the following assays:

- a. Cepheid Xpert Xpress SARS-CoV-2
 - b. Roche cobas SARS-CoV-2 real-time RT-PCR test (EUA200009/A001)
 - c. Abbott Molecular/RealTime SARS-CoV-2 assay (EUA200023/A001)
2. The flowchart for deriving the COVID-19 cases included below for the second VE endpoint in evaluable efficacy participants:

Asymptomatic Case Definition

An asymptomatic case is defined as positive N-binding antibody at a post-Dose 2 visit (eg, Visit 4, 1 month after Dose 2) in participants without serological or virological evidence of infection prior to that visit, determined by negative N-binding antibody at Visit 1 and negative NAAT at Visit 1 and Visit 2 and at the time of a potential COVID-19 illness. A secondary definition will be applied without the requirement for a negative NAAT at Visit 2.

Surveillance Times

For the asymptomatic cases based on N-binding antibody seroconversion, the start-of-surveillance times are summarized as follows:

Endpoint's Associated Participant-Level Population	Start-of-Surveillance Time
Evaluable efficacy (maternal)	Dose 2
Dose 2 all-available efficacy (maternal)	Dose 2
Dose 1 all-available efficacy (mITT) (maternal)	Dose 1

The end of a surveillance period for each participant is the earliest of the following:

- Date of the first positive N-binding antibody result after Dose 2.
- Date of the participant's last post-Dose 2 N-binding antibody test that is prior to a COVID-19 symptom associated with a nonnegative NAAT result.
- Date of the participant's last post-Dose 2 N-binding antibody test that is prior to an important protocol violation (for analysis based on the evaluable efficacy population).

Once the asymptomatic cases and surveillance periods have been identified, VE can be calculated as $100 \times (1 - \text{IRR})$, where IRR is the ratio of incidence of asymptomatic infection per 1000 person-years of follow-up for the active vaccine group to the placebo group.

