5.2.1. Analyses for Binary Data

Descriptive statistics for categorical variables (eg, proportions) are the percentage (%), the numerator (denoted by lowercase n) and the denominator (denoted by uppercase N) used in the percentage calculation, and the 95% CIs where applicable.

The exact 95% CI for binary endpoints for each group will be computed using the F distribution (Clopper-Pearson).¹ The 95% CI for the between-group difference for binary endpoints will be calculated using the Miettinen and Nurminen² method.

The 3-tier approach will be used to summarize AEs. Under this approach, AEs are classified into 1 of 3 tiers. Different analyses will be performed for different tiers:

- Tier 1 events: These are prespecified events of clinical importance and are identified in a list in the product’s safety review plan. No Tier 1 events have been identified to date for BNT162b2.
- Tier 2 events: These are events that are not Tier 1 but are considered “relatively common.” A MedDRA PT is defined as a Tier 2 event if there are at least 1% participants with the AE term in at least 1 vaccine group.
- Tier 3 events: These are events that are neither Tier 1 nor Tier 2.

For both Tier 1 (if any are identified during the study) and Tier 2 events, a 95% CI for the between-group difference in proportions will be calculated based on the Miettinen and Nurminen² method. In addition, for Tier 1 events (if any), the asymptotic p-values will also be presented for the difference in proportions, based on the same test statistic and under the assumption that the test statistic is asymptotically normally distributed. For Tier 3 events, counts and percentages for each vaccine group will be provided.

AEs and SAEs reported for maternal participants during the open-label follow-up period will be summarized separately.

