6.2.3.2. Adverse Events

6.2.3.2.1. Main Analyses

- Estimand: The percentage of infant participants reporting AEs from birth through 1 month of age (Section 2.1).
- Analysis set: Safety population (infant) (Section 4).
- Analysis time point: Birth through 1 month of age.
- Analysis methodology: Descriptive statistics and 3-tiered approach (Section 5.2.1).
- Intercurrent events and missing data: Missing data will not be imputed except for partial AE start dates (Section 5.3).
- Reporting results: Counts, percentages, and the associated Clopper-Pearson 95% CIs for infant participants with AEs from birth through 1 month of age will be provided for each vaccine group (according to the study intervention the maternal participants received). For both Tier 1 (if any) and Tier 2 events, the between-group difference in proportions and the associated 95% CI based on the Miettinen and Nurminen² method will be provided. For Tier 1 events (if any), the asymptotic p-values for the difference in proportions will be provided. For Tier 3 events, counts and percentages will be provided for each vaccine group (according to the study intervention the maternal participants received).

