6.2.3.3. Serious Adverse Events and AESIs

6.2.3.3.1. Main Analyses

- Estimand: The percentage of infant participants reporting SAEs and AESIs (major congenital anomalies, developmental delay) from birth through 6 months of age (Section 2.1).
- Analysis set: Safety population (infant) (Section 4).
- Analysis time point: Birth through 6 months of age.

- Analysis methodology: Descriptive statistics ([Section 5.2.1](#)).
- Intercurrent events and missing data: Missing data will not be imputed except for partial SAE start dates ([Section 5.3](#)).
- Reporting results: Counts, percentages, and the associated Clopper-Pearson 95% CIs for infant participants with SAEs and AESIs from birth through 6 months of age will be provided for each vaccine group (according to the study intervention the maternal participants received).

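### Should the infant COVID-19, MIS-C and 6-month SAE tables be split at the mother's unblinding?

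*SAP*

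**What the plan says.** Protocol 8.11.1.6 unblinds all mothers at the visit 21 to 35 days after delivery. Protocol 6.1.1 and 8.17 then give BNT162b2 to those who had placebo. The infant schedule (Protocol 1.3.3) runs to a last visit at day 160 to 200.

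SAP Appendix 2 ends vaccine-efficacy surveillance at unblinding. For the descriptive COVID-19 incidence rates in mothers and infants it keeps the same rules "except that unblinding at 1 month after delivery will not be considered as the end of the surveillance period". That sentence names COVID-19 incidence only; the end of MIS-C surveillance is not spelled out.

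The three infant tables are laid out as follows:

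- **COVID-19 (SAP 6.3.7.1.1):** counts, rates and intervals "will be provided for each vaccine group (according to the study intervention the maternal participants randomized" to. The only supplement is the second case definition.
- **MIS-C (SAP 6.3.8.1.1):** "incidence of MIS-C per 1000 person-years of follow-up, and the associated 2-sided 95% CIs will be provided for each vaccine group". There is no supplement.
- **SAEs and AESIs through 6 months (SAP 6.2.3.3.1):** counts and percentages "for each vaccine group (according to the study intervention the maternal participants received". The only further version is by breastfeeding status.

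For mothers there is a period split. SAP 5.2.1 states that "AEs and SAEs reported for maternal participants during the open-label follow-up period will be summarized separately", and SAP 6.4 repeats it. For infants, SAP 6.2.3.1 tabulates birth outcomes, and SAP 6.2.3.2.1 tabulates AEs by maternal group with "Analysis time point: Birth through 1 month of age".

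**The concern.** The SAP treats the mother's unblinding as a boundary in two places, maternal vaccine efficacy and maternal open-label safety, but not for her infant. Protocol 1.1 says infant safety will be evaluated in a similar way to maternal safety, so a reader could expect a matching infant split and take its absence for an oversight.

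The infant period before unblinding is also the only one that is both blinded and placebo-controlled. Afterwards the mother knows her allocation and may herself have been vaccinated if she was in the placebo group. If the two periods differed, a single rate would mostly show the later one. As an illustration with assumed values and a constant placebo rate, a rate ratio of 0.3 before unblinding and 1.0 after it would pool to between 0.105 × 0.3 + 0.895 × 1.0 = 0.93 and 0.219 × 0.3 + 0.781 × 1.0 = 0.85.

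The AE table to 1 month does not help for disease endpoints. Under Protocol 8.3.1 and 8.3.7, illnesses that meet the COVID-19 or MIS-C definitions are as a rule not recorded as AEs.

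**Working it through.** The documents state no figure for this point, so there is nothing to reproduce. The check measures how much follow-up is involved and what a split would show.

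**Inputs.** Unblinding day c = 21, 28 (midpoint) or 35 (Protocol 8.11.1.6). Last infant visit V = 160, 180 (midpoint) or 200 (Protocol 1.3.3). Group size 175 (Protocol 9.2), assuming one followed infant per mother and complete in-window visits.

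**Share of infant follow-up after unblinding, (V − c)/V**

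- c = 35, V = 160: 125/160 = 0.781
- c = 28, V = 180: 152/180 = 0.844
- c = 21, V = 200: 179/200 = 0.895

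The blinded share is therefore 10.5% to 21.9%. The share after a placebo mother actually receives Dose 3 depends on uptake, which is not given. At an assumed 70% it is 0.7 × 0.781 = 0.55 to 0.7 × 0.895 = 0.63.

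**Person-years per group, 175 × days/365.25**

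- Blinded block: 175 × 21/365.25 = 10.1 to 175 × 35/365.25 = 16.8
- Full period: 175 × 160/365.25 = 76.7 to 175 × 200/365.25 = 95.8

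**Precision with zero cases.** The exact two-sided 95% Poisson upper limit on the count is 3.689.

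- Blinded block: 3.689/16.77 = 220 to 3.689/10.06 = 367 per 1000 person-years
- 180 days: 3.689/86.2 = 43 per 1000 person-years

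Under a constant rate, if a group had 10 cases in all (an assumed total), about 1 to 2 would fall in the blinded block (10 × 0.105 to 10 × 0.219).

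**Endpoint by endpoint**

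- *COVID-19.* The objective in SAP 2.1 concerns infants of mothers vaccinated during pregnancy. In-utero exposure is settled at birth and is not altered by the mother's unblinding, so the full-period rate by randomized group answers it.
- *SAEs.* Protocol 10.2.2 requires an SAE to be an AE first, so early serious events fall within the 1-month AE table. That table uses a fixed age and does not label events as serious, but it is a close proxy for the blinded period.
- *MIS-C.* The case definition accepts COVID-19 exposure up to 4 weeks before onset. That 28-day lag is about as long as the whole 21-to-35-day block, so illness from a blinded-period infection could be counted after the split.
- *"Received" in the SAE table.* SAP 5.2 lets vaccine group mean randomized or received. The objective is vaccination in pregnancy, and SAP 6.6.2.1 refers to "Doses 3 and 4 for the original placebo group". Assigning infants by a postpartum dose would nearly empty the placebo column if uptake is high. The only sensible reading is the original two-dose series.

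**The case for a change.** The strongest case for a split concerns ascertainment. After unblinding, the mother and site staff know the allocation. She reports her infant's symptoms (Protocol 8.19) and takes the swab herself at a telehealth visit (8.19.1). Symptoms found only in the second definition trigger a visit at the principal investigator's discretion. Case review is blinded, but it comes after these steps. Maternal incidence carried past unblinding is confined to women randomized to BNT162b2, so the infant COVID-19 and MIS-C tables are the only disease-incidence tables comparing both groups beyond that point. The SAP also analyzes infants by breastfeeding status, so a placebo mother's later vaccination might matter. A split would be cheap, since dose dates are in the CRF and Dose 3 and 4 counts are planned.

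Much of this is accurate. No infant table isolates blinded-period COVID-19 cases, and knowledge of allocation could affect reporting. But these are reasons for caution in interpretation; they do not show that the planned tables mislead. The maternal parallel is weak: placebo mothers personally receive a new intervention after unblinding, whereas infants do not, and both SAP statements on the split are limited to mothers. The phrase in Protocol 1.1 about similar evaluation reads naturally as referring to counts, Clopper-Pearson intervals and the 3-tier approach.

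The split would also be harder to read than it appears. Period is confounded with infant age within each group, emergency unblinding could precede the 1-month visit, and the Dose 3 date may differ from the unblinding date if vaccination is delayed.

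**Conclusion.** No change is needed. Carrying infant COVID-19 surveillance past unblinding is an explicit choice that fits the vaccination-in-pregnancy objective. The COVID-19 and MIS-C rates are exploratory, infant safety is secondary, and everything is descriptive without hypothesis tests. It is true that 78.1% to 89.5% of infant follow-up falls after the mother's unblinding, but this measures follow-up time, not error.

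A split would add a block of 10.1 to 16.8 person-years per group, too small to alter any conclusion. For early SAEs it would largely duplicate the 1-month AE table, and for MIS-C it would not do what it is meant to do. The one display with some descriptive value, infant COVID-19 cases and person-time before and after the mother's actual unblinding date, can be produced at reporting if someone wants it. The plan is sound without it, and analysts can be expected to read the received group as the original series.

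The figures assume 175 followed infants per group and complete in-window visits; losses would make the blinded block smaller still.
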